#### **e) Withdrawal of Subjects**

Subjects may be withdrawn from the study because of failure to follow instructions of the research staff or if the principal investigator decides that the research study is no longer in the subject's best interest. Details are provided in the consent form.

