### **Control Group: (60 seniors).**

Seniors who are randomly assigned to the control group will continue receiving regular dental care under the standard clinic operation. Subjects in this group will complete intake forms to assess main behavioral outcomes, at baseline and after 12 months. No other activities will be conducted in this group.

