### **Data Management:**

All demographic information and questionnaires will be administered in person. Data will be entered into an excel spreadsheet. Data will be downloaded to an IBM-compatible computer and stored on a password-protected account, and it will be exported to a computer data analysis program (SAS/SPSS). Data will be cleaned and checked for errors prior to the analysis; imputation procedures for handling missing data will be conducted depending on the number of cases with missing data. Participant names and corresponding identification numbers will be stored separately in a locked file cabinet or password-protected file.

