### **Data Analysis:**

Initial analyses will be conducted to determine normality of distributions of the continuous variables, and any necessary transformations will be conducted. Primary outcomes will be the OHIP 14 and the self-efficacy scores. All eligible patients will be randomly assigned to 1 of the 3 groups described above. Although randomization should provide relatively comparable groups, demographic variables that differ between groups and are correlated with the primary outcomes will be used as covariates. Preliminary analysis will include measures of central tendency and dispersion, as well as an examination of the bivariate relationships among the primary and secondary outcome variables, potential moderators, and demographic characteristics.

Differences between the groups on baseline demographic, and psychological measures will be examined using  $\chi^2$  (Pearson) or Student's *t*-tests, as appropriate. Moreover, differences on the variables listed above among completers and drop-outs will also be explored. Intention to treat (ITT) analyses will then be conducted.

OHIP 14 and self-efficacy scores will be the primary outcomes. Initially, we will assess the differences between the interventions and control using 2-sample *t*-tests. The main analysis will be based on linear mixed-effects models for repeated measures (using the OHIP 14 and self-efficacy scores as continuous outcome variables) to assess differences between intervention and control groups. Similar analyses will be conducted for secondary outcome measures. Statistical significance will be set at  $p < .05$ .

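### Subjects may be withdrawn from the study for not following staff instructions, with no stated outcome follow-up afterwards; this is not reconciled with the intention-to-treat analysis

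*Combined protocol and SAP*

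**What the plan says.** Section 7(e), Withdrawal of Subjects, gives two grounds for withdrawal. The first is compliance: "Subjects may be withdrawn from the study because of failure to follow instructions of the research staff". The second is the principal investigator's judgement that continuing no longer serves the subject. The section then refers the reader elsewhere: "Details are provided in the consent form". The consent form is not among the material available for this review.

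The Data Analysis section says: "Intention to treat (ITT) analyses will then be conducted". It does not define the ITT set. It names the model ("The main analysis will be based on linear mixed-effects models for repeated measures"), with two-sample *t*-tests before it, and adds that "differences on the variables listed above among completers and drop-outs will also be explored". On missing values, the Data Management section says that "imputation procedures for handling missing data will be conducted depending on the number of cases with missing data"; it gives no method, threshold or missing-data assumption.

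The arms differ in what is asked of subjects. Controls complete forms "at baseline and after 12 months", and "No other activities will be conducted in this group". Intervention Group 1 is invited to two one-hour group sessions and is assessed at baseline, 6 and 12 months. Intervention Group 2 has three visits with a hygienist, with assessments at baseline, at each follow-up visit and at 18 months.

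**The concern.** ITT has two parts: analysing subjects in the arm to which they were randomised, and having outcomes for as many of them as possible. The plan states the first in general terms. The withdrawal rule works against the second, because someone withdrawn from the study would ordinarily not be asked for later questionnaires, and nothing available says otherwise.

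The ground for withdrawal is behaviour after randomisation. People who do not follow instructions may well differ in self-efficacy, oral-health quality of life or knowledge, which are the outcomes of this trial. Missing outcomes created in this way are unlikely to be a random subset.

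The rule may also fall unevenly. The education arms have more contacts, and so more occasions on which an instruction might not be followed. Allocation is described as concealed only until the patient agrees to take part, and no later blinding of staff is stated, so the discretion could be used with the arm known. If more people are withdrawn from an education arm, and they differ from those who stay, the comparison with control is biased. Questionnaires not collected at the time cannot be recovered later.

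**Working it through.** **1. Is there a figure in the plan to reproduce?** No. The documents give no withdrawal rate, SD, effect size or power. The arm sizes are 60 + 60 + 70 = 190, which agrees with the stated total. Ten of the 70 are calibration patients outside the study, which leaves 60 per arm.

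**2. Do the planned analyses repair the missing outcomes?**

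- *t*-tests: these use observed outcomes only, unless values are imputed.
- Mixed model: this uses data collected up to withdrawal. A control withdrawn before month 12, or a Group 1 subject withdrawn before month 6, contributes baseline only. Under missing at random, the model in effect treats withdrawn subjects like retained arm-mates with similar earlier scores. Withdrawal for non-adherence is where that assumption is most doubtful.
- Imputation: this is conditional and unspecified, and if based on missing at random it shares the same weakness.
- Comparison of completers with drop-outs: this describes the problem and does not correct it.

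**3. Illustration of size, on assumed values.** Let w be the share withdrawn from one education arm, wc the share withdrawn from control, and g the amount in SD by which withdrawn subjects score worse than those retained in the same arm. Assume no true effect, withdrawn subjects simply dropped, SD 1, and a two-sided 5% test (the plan does not state sidedness).

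If the whole arm has mean 0, the retained mean m satisfies (1 − w)m + w(m − g) = 0, so m = wg. Hence:

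- bias b = (w − wc)g
- SE = √[1/(60(1 − w)) + 1/(60(1 − wc))]
- type I error = Φ(−1.96 − b/SE) + 1 − Φ(1.96 − b/SE)

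| w | wc | g | bias (SD) | SE | type I error |
|---|---|---|---|---|---|
| 0.10 | 0 | 0.5 | 0.05 | 0.188 | 5.8% |
| 0.10 | 0 | 1.0 | 0.10 | 0.188 | 8.3% |
| 0.20 | 0 | 0.5 | 0.10 | 0.194 | 8.1% |
| 0.20 | 0 | 1.0 | 0.20 | 0.194 | 17.8% |
| 0.20 | 0.10 | 0.5 | 0.05 | 0.198 | 5.7% |
| 0.20 | 0.10 | 1.0 | 0.10 | 0.198 | 8.0% |
| 0.10 | 0.10 | 0.5 or 1.0 | 0 | 0.192 | 5.0% |

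For the last row of the first block: b = 0.20 × 1.0 = 0.20; SE = √(1/48 + 1/60) = 0.194; b/SE = 1.03; type I error = 0.001 + 0.177 = 0.178.

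**4. Effect of using baseline scores.** The table is an unadjusted comparison of completers, not the planned model. Suppose withdrawn subjects are equally worse at baseline and the baseline to follow-up correlation is r. Adjustment then leaves a bias of roughly (1 − r)wg when wc = 0. For r between 0.5 and 0.7 this runs from 0.3 × 0.05 = 0.015 SD to 0.5 × 0.20 = 0.10 SD. If they do not differ at baseline, adjustment removes nothing.

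**5. Loss of precision.** This is the smaller effect. With 60 controls, power for an assumed 0.5 SD difference falls from 78.2% (60 in the education arm) to 76.0% (54) and 73.3% (48).

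**The case against.** The case on the other side is substantial, and several parts of it stand.

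*A reader might infer that the rule contradicts ITT.* The documents do not support that. The withdrawal section governs participation and says nothing about the analysis set. Subjects withdrawn part-way can be analysed as assigned on the data they gave, and imputation is foreseen. What stands is a gap between the two sections.

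*A reader might infer that non-adherers will be removed, mainly from the education arms.* The wording is permissive, so removal is possible rather than certain. Attendance is by invitation, so declining a session is not plainly a failure to follow instructions. What counts as an instruction of the research staff is not defined, and Group 2 education is given by a hygienist whom the calibration section treats separately from those staff. Instructions about completing assessments would apply to all three arms. Uneven withdrawal is therefore a plausible inference, not a stated fact.

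*A reader might infer that the bias favours education.* This too is not established. Type I error rises only if withdrawn subjects differ in prognosis, and nothing in the documents shows the direction. People who disengage because their mouths are healthy would push the result the other way.

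*The consent form may cover follow-up after withdrawal.* It may, and its absence here is not a defect of the plan. Even so, the protocol's analysis text should say what happens to these subjects' outcomes.

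None of this answers the remaining point: the protocol states an adherence-related ground for leaving the study and, in the text available, does not provide for continued outcome collection.

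**Conclusion.** The concern holds in a limited form. A discretionary, post-randomisation, adherence-related withdrawal rule applies to the study as a whole and is not reconciled with the stated ITT analysis. It can create informative missing outcomes that the planned *t*-tests, mixed model and conditional imputation do not reliably repair. More frequent withdrawal from the education arms is plausible, given what each arm is asked to do, but it is not documented; the direction and size of any bias are unknown.

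The calculated range rests wholly on assumed inputs: the withdrawal rate, no control withdrawals, the deficit in those withdrawn, and a completers-only comparison. Its upper end is the extreme corner; the other three corners with no control withdrawals stay between 5.8% and 8.3%. This is a cheap improvement rather than a flaw that invalidates the trial.

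**What to change.** Reconcile section 7(e) with the Data Analysis section:

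1. Separate not taking part in the education activities from leaving outcome follow-up.
2. State that subjects withdrawn for failure to follow instructions are still asked, while their consent remains, to complete all remaining questionnaires.
3. Define the ITT set as all randomised subjects, analysed in their assigned arm.
4. Report withdrawals by arm and by reason.

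The ground concerning the subject's best interest is left as it stands, and no view is offered on when the education activities or visits should end for an individual. The cost is a sentence or so in the protocol and consent form, and follow-up questionnaires for a few more people.

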#### **f) Privacy & Confidentiality**

## ORAL HEALTH EDUCATION SENIORS

As in any type of treatment or clinical research program, patients' confidentiality must be carefully guarded and respected. The study will use Protected Health Information (PHI) and a HIPAA Authorization form is being submitted with this application (see Appendix D).

There will be a separate file with identifiers in receipt of the principal investigator. All data with identifying information will be stored in locked files or encrypted, password-protected electronic data storage. Data being analyzed will be identified by subject codes (using the subject identification number) and identifying information will be removed. The identity of patients will not be revealed in the presentation or publication of any results from this project. All assistants and others working on the project will be educated about the importance of strictly respecting patients' rights to privacy and confidentiality and will have completed training concerning proper practice in accordance with HIPAA regulations.

Protected Health Information that will be collected includes the patient's name, date they were seen for the study, phone number, and age. In addition, dental record number, medical and dental chart information related to oral hygiene behaviors and systemic diseases will be accessed from the dental chart for those assigned to intervention group 2. Only those subjects assigned to intervention group 2 will be given the HIPAA Authorization form to sign. The electronic PHI data will be downloaded to a computer using encrypted, password-protected storage of electronic data. All participants will receive a unique random identification number, which will correspond to that person's data. Participant names and corresponding identification numbers will be stored separately in a locked file cabinet or encrypted, password-protected storage of electronic data.

### **8) Risks to Subjects**

No risks are expected to the subjects. All clinical activities are part of regular dental treatment provided to patients in the normal course of dental treatment.

### **9) Potential Benefits to Subjects**

Patients will be educated about oral health risky behaviors and oral hygiene techniques in this study. There are no other direct benefits to the subject from this study.

### **10) Costs to Subjects**

Not Applicable

### **11) Informed Consent**

See Consent Form (Appendix A and D) submitted with this protocol. Study will follow "HRP-802 INVESTIGATOR GUIDANCE: Informed Consent" to obtain informed consent.

Seniors who provide consent and complete entire participation in the study will be entered into a raffle to receive a \$350-dollar gift card. This information has been included into the consent form.

### **12) Vulnerable Populations**

## ORAL HEALTH EDUCATION SENIORS

The study involves does not involve a vulnerable population as defined by IRB regulations.

### **13) Compensation for Research-Related Injury**

Not applicable

### **14) Economic Burden to Subjects**

Not applicable

### **15) Drugs or Devices**

Not applicable.

### **16) Multi-Site Human Research**

Not applicable

### **17) Sharing of Results with Subjects**

Results of the study can be provided to the participants, if requested. No other data will be shared with the subjects.

### Appendix (B) Flyer

# Interested in joining a research study?

If so, you may be eligible to participate in a research study investigating the efficacy of various oral health education strategies

For your participation, you will be entered in a contest to win a \$350 gift card.  
Seniors 55 years old and older may be eligible for participation

**Appendix C Measurement Instruments**

**(Demographics)**

---

A1. What is the 5-digit ZIP code at your home address?

[ \_ \_ \_ \_ \_ ]

A2. What is your gender?

[ \_ ]

1) \_\_ Male

2) \_\_ Female

A3. What is your age in years?

[ \_\_\_\_\_ ]

A5. What is the highest grade of school that you completed?

[ \_ ]

1)        \_\_ less than high school (grades 0-8 )

ORAL HEALTH EDUCATION SENIORS

- 2)  Some high school (grades 9-11)
- 3)  High school graduate (grades 12 or GED)
- 4)  Some college (include vocational, trade, or technical school after college, associate degree, No four-year degree )
- 5)  College graduate ( BS or other four year degree)
- 6)  Post graduate or professional school after college

A6. What is your family's income level?

- 1)  Less than \$19,999
- 2)  \$20,000 - \$49,999
- 3)  More than \$50,000

A9. What race do you consider yourself to be? *(Place a check next to the correct answer)*

- 1)  White or Caucasian or European American
- 2)  Black or African American
- 3)  American Indian or Alaska Native
- 4)  Asian
- 5)  Native Hawaiian or Other Pacific Islander
- 6)  Other ( \_\_\_\_\_ )

A10. Are you of Hispanic or Latino origin or descent?

- 1)  Yes
- 2)  No

**Oral Health Self Efficacy Scale**

Seniors oral health self-efficacy measure:

*Oral Health Self-efficacy (OHSE) - Scale: 4=very confident, 1=not at all confident.*

1. under a lot of stress
2. depressed
3. anxious
4. feeling like you do not have the time (too busy)
5. tired
6. worrying about other things in your life
7. bothered by your crying child
8. bothered because your child doesn't stay still when you want him or her to brush

ORAL HEALTH EDUCATION SENIORS

9. told by your child that he/she does not feel like brushing right now

**ORAL HEALTH IMPACT PROFILE SHORT VERSION OHIP-14\***

**Question**

1. Have you had trouble *pronouncing any words* because of problems with limitation your teeth, mouth or dentures?
- |       |             |              |              |            |
|-------|-------------|--------------|--------------|------------|
| 0     | 1           | 2            | 3            | 4          |
| Never | Hardly Ever | Occasionally | Fairly Often | Very Often |
2. Have you felt that your *sensitivity of taste* has worsened because of problems with your teeth, mouth or dentures?
- |       |             |              |              |            |
|-------|-------------|--------------|--------------|------------|
| 0     | 1           | 2            | 3            | 4          |
| Never | Hardly Ever | Occasionally | Fairly Often | Very Often |
3. Have you had *painful aching* in your mouth?

ORAL HEALTH EDUCATION SENIORS

0            1            2            3            4  
Never            Hardly Ever    Occasionally    Fairly Often    Very Often

4. Have you found it *uncomfortable to eat any foods* because of problems with your teeth, mouth or dentures?

0            1            2            3            4  
Never            Hardly Ever    Occasionally    Fairly Often    Very Often

5. Have you been *self-conscious* because of your teeth, mouth or dentures?

0            1            2            3            4  
Never            Hardly Ever    Occasionally    Fairly Often    Very Often

6. Have you *felt tense* because of problems with your teeth, mouth or dentures?

0            1            2            3            4  
Never            Hardly Ever    Occasionally    Fairly Often    Very Often

7. Has your *diet been unsatisfactory* because of problems with your teeth, disability mouth or dentures?

0            1            2            3            4  
Never            Hardly Ever    Occasionally    Fairly Often    Very Often

8. Have you had to *interrupt meals* because of problems with your teeth, mouth or dentures?

0            1            2            3            4  
Never            Hardly Ever    Occasionally    Fairly Often    Very Often

9. Have you found it *difficult to relax* because of problems with your teeth, disability mouth or dentures?

0            1            2            3            4  
Never            Hardly Ever    Occasionally    Fairly Often    Very Often

10. Have you been a bit *embarrassed because* of problems with your teeth, mouth or dentures?

0            1            2            3            4  
Never            Hardly Ever    Occasionally    Fairly Often    Very Often

11. Have you been a bit *irritable with other people* because of problems with disability your teeth, mouth or dentures?

0            1            2            3            4  
Never            Hardly Ever    Occasionally    Fairly Often    Very Often

12. Have you had *difficulty doing your usual jobs* because of problems with your teeth, mouth or dentures?

## ORAL HEALTH EDUCATION SENIORS

0            1            2            3            4  
Never            Hardly Ever    Occasionally    Fairly Often    Very Often

13. Have you felt that life in general was *less satisfying* because of problems with your teeth, mouth or dentures?

0            1            2            3            4  
Never            Hardly Ever    Occasionally    Fairly Often    Very Often

14. Have you been *totally unable to function* because of problems with your teeth, mouth or dentures?

0            1            2            3            4  
Never            Hardly Ever    Occasionally    Fairly Often    Very Often

### Seniors Oral Health Knowledge Assessment

Statements to be evaluated with a three-point Likert Scale (yes, no, and don't know)

1. "Health of mouth is directly related to body"
2. "You can chew just as well with denture tooth as with your natural teeth"
3. "When gums bleed during brushing, it is best to leave them alone"
4. "Older adults with dry mouth get more cavities"
5. "The most common cause of dry mouth is medication"
6. "Older adults with teeth need to use fluorides"
7. "Mouth rinsing is a good alternative to daily tooth brushing"
8. "People with no teeth need to be seen by a dentist"
9. "Dentures should be removed for few hours every day"
10. "Dentures those don't fit well can cause oral cancer"
11. "It is normal for residents to have pain and sores in their mouth"
12. "Residents who do not cooperate for daily mouth care are best left alone"

ORAL HEALTH EDUCATION SENIORS

13. "Dental check-ups are as important as medical"
14. "Residents can lose their teeth if they remain dirty"
15. "As people get old they naturally lose their teeth"
